10.1.3 Analysis of the Secondary Endpoints

CSF Inflammatory Cytokine Analysis: Non-parametric 2-sided tests will be used to detect differences in CSF inflammatory cytokine increases from before surgery to 24 h after surgery in CN-105 vs placebo treated patients. For our primary analysis, we will group all three CN-105 drug dose groups together into one larger group of ≥ 117 CN-105 treated patients. In unpublished data from the MADCO-PC study, we observed a pre- to 24 h post-op CSF IL-6 change of 21.55 pg/ml (SD=44.72; log normal distribution; see Supplement Appendix Figure 2). Markov-chain Monte Carlo simulations based on these data demonstrate that this study (with ≥ 117 CN-105 treated and ≥ 39 placebo treated patients) will have $>80\%$ power (with $\alpha=0.05$) in a 2-sided Wilcoxon Rank Sum test to detect a 34% smaller increase in IL-6 levels from before to 24 h after surgery in CN-105 vs placebo treated patients. Based on our preliminary MADCO-PC data, this sample size will also provide $>80\%$ power to detect a 36% smaller increase in G-CSF, a 32% smaller decrease in IL-8, and a 44% smaller decrease in MCP-1 levels from before surgery to 24 h after surgery in CN-105 vs placebo-treated patients. A post-hoc Kruskal-Wallis analysis will be used to compare the change in each of these inflammatory cytokines from before surgery to 24 h after surgery by CN-105 dose level. We will also examine CSF inflammatory cytokine levels 6 weeks +/- 3 weeks after surgery in all study patients to evaluate whether CN-105 treatment results in a long lasting reduction of CSF inflammatory cytokine levels.

Cognitive Data Analysis: We will compare continuous cognitive index change scores (Newman MF et al, 2001) between patients who receive CN-105 vs placebo using a 2-sided t-test. Based on the cognitive change variance seen in MADCO-PC patients (SD=0.21), this study (with ≥ 117 CN-105 treated and ≥ 39 placebo treated patients) will provide 80% power with $\alpha=0.05$ to detect a half SD difference (i.e. 0.1 units) in CCI score between CN-105 vs placebo treated patients. Post-hoc ANOVA will determine if there are differences in cognitive index values by CN-105 dose level. We will also perform a chi-squared analysis (or Fisher’s exact test if needed) to determine whether the rate of POCD as a dichotomous outcome (defined by a 1 SD drop in any of the 4 cognitive domains we have previously studied- 1- verbal memory, 2- visual memory, 3- attention/concentration, and 4- executive function) differs between CN-105 vs placebo treated patients.

Delirium analysis: Patients will be divided into those with delirium (i.e., 1 or more positive delirium

assessments) vs those without delirium (no positive delirium assessments). We will compare delirium rates between CN-105 treated and placebo treated patients using a two-sided chi-square test. With an expected delirium rate of 40% in placebo treated patients, this study (with >117 CN-105 treated patients, and >39 placebo treated patients) will provide 80% power to detect a 25% lower absolute rate of delirium in CN-105 vs placebo treated patients. Post-hoc ANOVA testing will evaluate for differences in delirium rates between CN-105 drug dose level groups, with post-hoc pairwise comparison tests as appropriate. Additional post-hoc analyses will evaluate delirium duration and severity between CN-105 vs placebo treated patients.

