10.2 Sample Size

We planned to enroll up to 250 patients total in this phase 2 escalating dose study, to obtain three successive groups of 67 randomized patients each. *Because enrollment happens at consent, and not all patients that consent will be randomized, we will keep enrolling patients until we reach 67 consented and randomized patients in each cohort.* In each group of 67 patients, 50 will receive a given dose of CN-105 and 17 will receive placebo. In our recent MADCO-PC study, ~80% of patients returned for the 6 week assessment. Thus, enrolling 67 patients in each group ensures ≥ 52 patients (i.e. 39 CN-105-treated; 13 placebo-treated) will complete the 3 month postop assessment. Due to a clerical error by the Investigational Drug Services that prepares our drug/placebo doses, 69 patients were randomized to the first patient cohort rather than 67. There will be no baseline preoperative cognitive status inclusion/exclusion criteria. Our prior work suggests ~15% of Duke orthopedic surgery patients over age 60 have MCI, ~5% have dementia, and ~80% are cognitively normal. All primary analyses here will be performed on patients grouped together (independent of baseline cognitive status); exploratory analyses will examine effects stratified by baseline cognitive strata, dose level, and by APOE4 carrier status.

Given the aforementioned expected 5% AE rates in placebo-treated patients, at completion we will have >80% power (with $\alpha=0.05$) in a two-sample two-sided unpooled variance chi-square test to detect an absolute difference of 14.8% between grade II or higher AE rates seen in placebo vs CN-105 treated patients (pooling the three dose levels of CN-105 together). We will also track the rates of other grade II or higher AEs recorded by the patient's surgical team in the medical record; at study completion we will use 2-sided t tests to compare the rates of any other grade II or higher AEs between placebo vs CN-105 treated patients.

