10.3 Measures to Minimize Bias

10.3.1 Enrollment/Randomization/Masking Procedures

Participants will be randomized to receive either CN-105 or placebo after they consent to participate in the trial, within 1 week prior to their index surgery. Participants will be enrolled in 1 of 3 dose cohorts (see [Table 1](#)) of 67 subjects each. An independent statistician will prepare dose stratified mixed block size randomization lists in a 3 to 1 ratio to achieve the desired distribution of drug and placebo. In each block of 67 trial participants, 50 will receive a given dose of CN-105 and 17 will receive placebo, in a double-blind fashion. CN-105 will be dissolved in normal saline, and either it or normal saline placebo will be administered as an IV drip over 15-30 minutes. Due to a clerical error by the Investigational Drug Services that prepares our drug/placebo doses, 69 patients were randomized to the first patient cohort rather than 67. Additionally, *because enrollment happens at consent, and not all patients that consent will be randomized, we will keep enrolling patients until we reach 67 consented and randomized patients in each of the last two cohorts.*

CN-105 and placebo will be prepared in identical bags labelled simply with the trial participant's number (1–203) to keep all trial staff and clinicians blinded to randomization. Only the

MARBLE Study – Protocol Version 7**PI: [name], PhD**

investigational pharmacist will have the randomization list that explains which drug (CN-105 or placebo) each participant is to receive and what dose of CN-105 or placebo will be administered every 6 hours (+/- 90 minutes) starting within 1 h before the scheduled or actual start of anesthesia/surgery and continuing until the end of postoperative day 3 (or when the participant is discharged home, whichever comes first), up to a maximum of 13 doses. Each case start time will be defined by the study team as either the start of the surgery/procedure or the start of anesthesia. In order to minimize bias, investigators conducting the laboratory assays on the CSF and blood samples will be blinded to trial group assignment during the course of the trial.

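### The 24 h CSF cytokine comparison is a valid but unadjusted rank test; adjusting for the scheduled baseline level could add power at little cost, and no effect estimate with CI is named

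*Combined protocol and SAP*

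**What the plan says.** Section 10.1.3 (Analysis of the Secondary Endpoints) sets out the comparison: "Non-parametric 2-sided tests will be used to detect differences in CSF inflammatory cytokine increases from before surgery to 24 h after surgery". For the main comparison, "we will group all three CN-105 drug dose groups together into one larger group", giving at least 117 CN-105 and at least 39 placebo participants. The power statement rests on IL-6 data from the earlier cohort (MADCO-PC): "we observed a pre- to 24 h post-op CSF IL-6 change of 21.55 pg/ml (SD=44.72; log normal distribution". It claims more than 80% power at two-sided 0.05 "in a 2-sided Wilcoxon Rank Sum test to detect a 34% smaller increase in IL-6 levels from before to 24 h after surgery".

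No baseline cytokine covariate, cohort term or effect estimate with a confidence interval is named for this endpoint. The other cytokine analyses are a post-hoc Kruskal-Wallis test by dose level and a look at the 6-week levels. Section 10.2 adds exploratory stratification by cognitive status, dose level and APOE4 status, but not by baseline cytokine level.

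Two design facts bear on this. Section 4.1 schedules a CSF sample before surgery as well as at 24 h. Section 10.3.1 describes "mixed block size randomization lists in a 3 to 1 ratio", prepared separately by dose, so each cohort carries its own concurrent placebo group.

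**The concern.** A change score subtracts the baseline but does not remove the association between baseline and change. If participants with a high preoperative level tend to have larger (or smaller) rises, that predictable variation stays in the comparison as noise. Any participant with a computable change has a baseline value, so using it as a covariate loses nobody. The same holds for dose cohort: cohorts are enrolled one after another and randomisation is within cohort, yet the pooled test ignores this. Because allocation is 3:1 in every cohort, the omission is a matter of precision and not of bias.

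The secondary objective in Section 3.2 asks whether the drug blocks postoperative neuroinflammation, which is a question of size. A rank-sum p-value does not answer it unless an estimate and interval are reported with it. The plan promises a 95% confidence interval for dosing feasibility (Section 10.1.2) but none here.

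**Working it through.** **Inputs from the documents.** IL-6 change: mean 21.55 pg/ml, SD 44.72, log-normal; target a 34% smaller increase; two-sided 0.05; 117 vs 39 (all Section 10.1.3). The 117 and 39 are 3 × 39 and 3 × 13, from Section 10.2, where "80% of patients returned for the 6 week assessment". No completion rate is given for the 24 h sample.

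**Input not in the documents.** The correlation r between log baseline and log change. It is an assumption, varied from 0 to 0.7.

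**Step 1: log-normal parameters.** σ² = ln(1 + (SD/mean)²); median = mean / exp(σ²/2).
- Placebo: SD/mean = 44.72/21.55 = 2.075; σ² = ln(5.306) = 1.669; σ = 1.292; median 9.36 pg/ml.
- CN-105, mean 34% lower with SD held: mean 0.66 × 21.55 = 14.22; SD/mean = 3.144; σ² = ln(1 + 3.144²) = 2.387; σ = 1.545; median 4.31 pg/ml.

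**Step 2: the plan's own power figure.** Simulated power of the unadjusted Wilcoxon test at 117 vs 39 depends on how a 34% smaller increase is read:
- mean 34% lower, SD held at 44.72: 82.4% (80.0% at a 33% reduction), which agrees with the stated figure;
- every change multiplied by 0.66: about 40%;
- additive shift of 0.34 × 21.55 = 7.33 pg/ml: about 98%.

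The first reading is used below because it is the one that lands close to the stated power. It implies a fall in the median of 1 − 4.31/9.36 = 54%.

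**Step 3: add the baseline.** Same change data, with rank ANCOVA (Quade's method: regress the ranks of change on the ranks of baseline, then compare the residuals between arms). The last column is the equivalent gain in sample size, 1/(1 − r²) − 1.

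| Assumed r | Wilcoxon power | Rank ANCOVA power | Gain (points) | Equivalent gain in N |
|---|---|---|---|---|
| 0 | 82.7% | 82.6% | 0 | 0% |
| 0.2 | 83.7% | 85.1% | 1 | 4% |
| 0.3 | 83.9% | 86.9% | 3 | 10% |
| 0.5 | 83.1% | 91.1% | 8 | 33% |
| 0.7 | 82.8% | 97.6% | 15 | 96% |

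Across repeat simulations the gain was about 0 points at r = 0, 2 to 4 at 0.3 and 7 to 11 at 0.5. Rejection under the null stayed near 5% for both tests. The reduction detectable with 80% power moves from about 33% unadjusted to about 32% (r = 0.3), 29 to 30% (r = 0.5) and 25% (r = 0.7). On the proportional reading, Wilcoxon power of about 40% becomes about 42% at r = 0.3 and 49% at r = 0.5. No cohort effect was simulated, so these figures concern the baseline covariate only.

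**Step 4: ANCOVA of the log 24 h level on log baseline.**
- If the pre- and postoperative concentrations are themselves log-normal (assumed baseline median 3 to 10 pg/ml, 50% lower postoperative level), it beats the Wilcoxon test on the difference by about 1 to 10 points.
- If the change is log-normal, as Section 10.1.3 states, and is added to an assumed log-normal baseline (first reading of Step 2), it has 57 to 70% power against 82% for Wilcoxon at r = 0, and is still lower at r = 0.3.

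**The case against.** The strongest defence is that a pre-specified two-sided rank test on skewed change scores is valid, matches the stated endpoint (an increase) and matches the stated power calculation. That stands. It is also fair that the analysis scale is not written out (the pg/ml difference is inferred from the power inputs), that a Hodges-Lehmann estimate with interval can accompany a rank-sum test without a new model, and that dose is not ignored altogether, since post-hoc and exploratory analyses by dose are planned.

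A reader might infer that the plan demonstrably gives up power and that log-scale ANCOVA should replace the rank test. The documents do not support this. They call the IL-6 change log-normal, not the 24 h concentration, and under that model log-scale ANCOVA can do clearly worse (Step 4). Which method wins depends on the baseline level, the correlation and the form of the effect, none of which is given. A distribution is stated for IL-6 only; the targets for IL-8 and MCP-1 are described as smaller decreases, and nothing shows that a log-linear model suits them.

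This objection does not reach rank ANCOVA. That method keeps the same change score and the same freedom from distributional form, and it matched or beat the unadjusted test, within simulation error, in every setting tried.

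**Conclusion.** The point holds as a missed efficiency gain and a missing effect estimate on a secondary endpoint. It is not an error in the test. Under the plan's IL-6 mean and SD, with the SD held, baseline-adjusted rank analysis adds about 0 points of power at r = 0, 2 to 4 at r = 0.3 and 7 to 11 at r = 0.5. If r is small the gain is negligible.

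Three further inferences go beyond the documents. A baseline value for every participant is scheduled but not guaranteed, although every computable change score has one. The endpoint is secondary; the primary endpoint is grade II or higher adverse events. And the plan is not shown to miss its own target for want of adjustment, since more than 80% is reached on the first reading of Step 2. The dependence of that figure on the reading of a 34% smaller increase is a separate matter. It does mean that spare power should not be assumed.

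**What to change.** Before unblinding, which Section 10.3.2 places after the final data set is locked, amend Section 10.1.3 as follows:
- Make the main 24 h comparison for each cytokine a rank ANCOVA (Quade) of the pre-to-24 h change with baseline level as covariate, stratified by dose cohort. State the scale of the change.
- Keep the unadjusted Wilcoxon rank-sum test as a sensitivity analysis.
- Report an effect estimate with 95% CI: a Hodges-Lehmann shift, or a geometric mean ratio from a supporting ANCOVA of log 24 h level on treatment, log baseline and cohort.
- Do not make log-scale ANCOVA the main model unless the earlier cohort's data show that it fits each cytokine. That cohort of 140 patients had pre- and postoperative CSF measurements (Section 2.2), so the sponsor can also estimate and report r from it.

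The cost is wording and slightly more analysis work, with no new samples, visits or participants. The existing power statement would still refer to the unadjusted test, and the text should say so.

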Summary:	
Participants age 60 and over who are scheduled to undergo non-cardiac, non-neurologic surgical procedures that will take more than 2 hours, and who will be admitted to the hospital after surgery, will be prospectively approached for enrollment in this trial. Participants will undergo preoperative cognitive testing and will be randomized to receive either the apolipoprotein E (apoE) mimetic peptide CN-105 or placebo. Three sequential cohorts of 67 patients will be randomized to receive CN-105 vs placebo; the CN-105 patients in each successive cohort will receive a higher/escalated dose of CN-105. Thus, we will enroll at least 201 participants to reach the target of 150 participants who complete the trial.
 
Trial participants will undergo cognitive testing and complete quality-of-life (QOL) assessments before surgery and again 6 weeks +/- 3 weeks after surgery. These participants will receive either 1 of 3 dose levels of CN-105 or placebo, within one hour prior to case start time and continuing every 6 hours until postoperative day 3 or hospital discharge (whichever occurs first). We will also record noninvasive scalp electroencephalogram (EEG) data from these participants immediately before, during and after surgery. Cerebrospinal fluid (CSF) (up to 20 ml) and blood samples (up to 10 mL) will be collected prior to surgery (between the time of consent and the time the surgery will start), 24 +/- 2 hr after the scheduled surgery start/anesthesia induction and 6 weeks +/- 3 weeks after the scheduled surgery start/anesthesia induction. Cerebrospinal fluid samples will be assayed for amyloid beta, tau, and other Alzheimer's disease (AD)-associated markers, as well as inflammatory cytokines and markers; blood samples will be assayed for serum inflammatory markers and used for APOE genotyping studies. CN-105 levels will also be measured in both CSF and peripheral blood samples. Trial participants will return to the hospital 6 weeks +/- 3 weeks later to undergo repeat cognitive testing and CSF/blood draws.

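### The post-hoc dose tests compare drug patients across successive cohorts without each cohort's own placebo patients, so a calendar shift cannot be told apart from a dose difference

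*Combined protocol and SAP*

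**What the plan says.** The Protocol Summary sets the structure: "Three sequential cohorts of 67 patients will be randomized to receive CN-105 vs placebo", with the dose raised in each successive cohort (also Sections 4.1 and 6.2.2). Section 10.2 gives the allocation: "In each group of 67 patients, 50 will receive a given dose of CN-105 and 17 will receive placebo". Section 10.3.1 describes "dose stratified mixed block size randomization lists in a 3 to 1 ratio". The first cohort ended at 69 patients after a pharmacy error. Nobody is randomised between doses.

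Section 10.1.3 names three dose analyses, all described as post-hoc:

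- Cytokines: "A post-hoc Kruskal-Wallis analysis will be used to compare the change in each of these inflammatory cytokines", from before surgery to 24 hours, by dose level.
- Cognition: "Post-hoc ANOVA will determine if there are differences in cognitive index values by CN-105 dose level".
- Delirium: "Post-hoc ANOVA testing will evaluate for differences in delirium rates between CN-105 drug dose level groups", followed by pairwise tests as appropriate.

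Leaving placebo out is explicit for delirium. It is the natural reading, though not the only possible one, for the other two.

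Sections 4.1 and 10.2 also promise exploratory analyses of effects stratified by dose level, with no method. The main efficacy comparisons pool the three doses.

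**The concern.** The only randomised evidence about a dose is its contrast with the placebo patients of the same cohort. A test across the three drug groups drops that contrast and compares enrolment periods as much as doses. A shift between cohorts in case mix, assay runs or mode of testing would enter the result in full, although the trial already holds the patients who could remove it.

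The documents make some drift plausible. Section 4.1 allows up to 72 months in total, counting completion of all activities. It also lets the 6-week cognitive testing move to remote video because of the pandemic, which bears on the cognitive index. Eligible surgery is broad and spans three hospitals. Section 7.3.3 lets assays run at the institution or in a collaborator's laboratory.

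At stake is whether any statement about differences between doses rests on a randomised comparison.

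**Working it through.** **Plan's own figure.** None. The documents give no power, alpha or sample size for any dose-level test, so there is nothing to reproduce.

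**Inputs from the documents.** Per cohort, 50 drug and 17 placebo patients randomised, or 39 and 13 completing (Section 10.2, where "80% of patients returned for the 6 week assessment"). Placebo delirium rate 40%; cognitive index SD 0.21; IL-6 change with mean 21.55 and SD 44.72 pg/ml, log-normal; two-sided 5% (Section 10.1.3).

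**Assumption.** There is no drug effect, and the same calendar drift acts on drug and placebo patients. The documents give no drift size, so a range is shown.

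**Step 1: delirium by formula.** For three groups of n, the omnibus test on 2 degrees of freedom (critical value 5.99) has noncentrality λ = n·Σ(p_j − p̄)² / [p̄(1 − p̄)].

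- 40/35/30%, n = 50: 50 × 0.005 / (0.35 × 0.65) = 1.10, rejection 14.2%. With n = 39: 0.86, 12.0%.
- 40/30/20%, n = 50: 50 × 0.02 / (0.30 × 0.70) = 4.76, rejection 48.3%. With n = 39: 3.71, 38.9%.

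**Step 2: cognitive index by formula.** λ = n·Σ(μ_j − μ̄)² / SD². For drift 0, 0.05, 0.10 and n = 39: 39 × 0.005 / 0.0441 = 4.42. The F test on 2 and 114 degrees of freedom rejects 44.3%.

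**Step 3: IL-6 inputs.** σ² = ln[1 + (44.72/21.55)²] = 1.669, so σ = 1.292; μ = ln 21.55 − 1.669/2 = 2.236. Drift multiplies the change by 1, 0.83 and 0.66 in cohorts 1 to 3 (a 34% fall).

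**Step 4: simulation.** The planned test is set against a treatment-by-cohort interaction F test that uses each cohort's own placebo (log scale for IL-6). Runs: 20,000 for delirium, 3,000 for IL-6, 8,000 for the cognitive index. Entries are rates of a false dose finding.

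| Drift, no drug effect | Per cohort | Planned test | Own-cohort placebo |
|---|---|---|---|
| Delirium 40/35/30% | 50+17 | 14.3% | 5.0% |
| | 39+13 | 11.9% | 4.9% |
| Delirium 40/30/20% | 50+17 | 48.6% | 5.0% |
| | 39+13 | 39.4% | 5.0% |
| IL-6 change down 34% | 50+17 | 25.5% | 4.9% |
| | 39+13 | 20.8% | 5.0% |
| Cognitive index, 0.05 | 39+13 | 14.8% | 4.7% |
| Cognitive index, 0.10 | 39+13 | 44.0% | 5.2% |

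The formulas in Steps 1 and 2 agree with the simulation. With no drift, the planned tests reject 4.3% to 5.2% of the time. If the Kruskal-Wallis test is read as including pooled placebo as a fourth group, it still rejects 17.5% to 21.9% at the 34% IL-6 fall, because pooling placebo over cohorts discards the matching in time.

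**Step 5: cost of using concurrent placebo.** The variance of a between-dose contrast is multiplied by (1/n_drug + 1/n_placebo) / (1/n_drug): 1 + 50/17 = 3.94, or 1 + 39/13 = 4.0. For the cognitive index, dose 3 against dose 1, the 95% half-width goes from 1.96 × 0.21 × √(2/39) = 0.093 to 1.96 × 0.21 × √(2/39 + 2/13) = 0.186. For delirium at a true 35/25/15% on drug and 40% on placebo (50+17), the power to show a dose difference falls from about 54% to about 18-25%, depending on the test.

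**The case against.** The case against is substantial.

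- **Status.** The three tests are post-hoc. Section 4.1 makes primary analyses independent of dose level and dose-level analyses exploratory. This stands and limits the weight of the point.
- **Placebo-referenced text elsewhere.** Section 4.2.1 words the primary safety endpoint as each dose cohort against placebo, and the DSMB sees drug against placebo after every cohort. Both concern adverse events. The stratified effects promised in Sections 4.1 and 10.2 have no method, so the only methods named for efficacy by dose remain those in 10.1.3.
- **Unknown drift.** No section reports a shift between cohorts. Remote testing could affect the cognitive index but not CSF cytokines, and the reduced EEG recording touches none of these endpoints. This stands: the rates above are conditional.
- **Power.** The replacement would usually miss a real dose difference of the size in Step 5. This also stands, but the planned test's higher power is valid only if drift is zero.

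A reader might also infer that ANOVA on yes/no delirium is itself an error that feeds the bias. It is unconventional wording, but it rejected as often as the chi-square test, to three decimals, in every scenario. Chi-square or logistic regression on drug patients alone would leave the confounding untouched. Nor do the documents call for an ordered trend test: they claim no monotone response, and a trend test on drug patients alone has the same confounding.

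**Conclusion.** The point holds for the dose-level tests only. Among drug patients, dose is fully confounded with enrolment period, and the named tests do not use the concurrent placebo patients who could separate the two. Under the assumed drifts, the false-positive rate of a nominal 5% test is about 12-14% for a 10-point fall in delirium, 39-49% for a 20-point fall, and 21-26% for a 34% fall in the IL-6 change. With no drift it is 5%.

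Three stronger readings are not supported. The main results are not at issue, because the pooled drug-versus-placebo comparisons keep about the same 3:1 ratio in every cohort. The documents do not say that these tests will choose a dose for a later trial. And because the tests are omnibus, drift would appear as a difference between dose groups; it would look like a dose response only if the shifts happened to be ordered.

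**What to change.** In Section 10.1.3, replace the drug-only dose tests as the basis for any statement about dose. For each endpoint fit one model with treatment, cohort and treatment by cohort: logistic for delirium, and a linear model for the cognitive index and for cytokines on a suitable scale, with baseline adjustment where available. Report each dose against the placebo patients of its own cohort with a 95% interval, and label the analysis exploratory. This also supplies the missing method for the effects by dose level promised in Sections 4.1 and 10.2. If the Kruskal-Wallis and ANOVA results are kept, label them as non-randomised comparisons across enrolment periods.

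No new data are needed; the change is to wording. The plan should state the price openly: each estimate rests on 13 to 17 placebo patients, with the variance and power costs in Step 5. The trial can describe each dose against placebo, but it has little power to separate the doses.

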4 TRIAL DESIGN AND ENDPOINTS

4.1 Description of Trial Design

Trial initiation will start with the enrollment of the first participant, which will occur only after the external institutional review board (IRB) as well as the Duke University Medical Center IRB has approved the protocol.

Participants age 60 and over who are scheduled to undergo non-cardiac, non-neurologic surgical procedures that will take more than 2 hours and who are scheduled to be admitted to the hospital after surgery at Duke University Medical Center (DUMC) or one of its affiliate hospitals (Duke Regional Hospital, Duke Raleigh Hospital) will be prospectively enrolled in this trial.

Trial participants will undergo cognitive testing and complete QOL assessments within 2 months before surgery and again 6 weeks +/- 3 weeks after surgery. These participants will receive either CN-105 or placebo, within one hour before the scheduled or actual start time of surgery and continuing every 6 hours through postoperative day 3 (up to 13 doses maximum) or hospital discharge, whichever occurs first. Each case start time will be defined by the study team as either the start of the surgery/procedure or the start of anesthesia.

We planned to enroll up to 250 patients in this phase 2 escalating dose study, with escalating CN-105 doses occurring in three successive groups of 67 randomized patients each. Due to a clerical error by the Investigational Drug Services that prepares our drug/placebo doses, 69 patients were randomized to the first patient cohort rather than 67. [Additionally, because enrollment happens at consent, and not all patients that consent will be randomized, we will keep enrolling patients until we reach 67 consented and randomized patients in each of the last two cohorts.](#)

In each group of 67 patients, 50 will receive a given dose of CN-105 and 17 will receive placebo. In our recent MADCO-PC study(Duke IRB protocol #45180), ~80% of patients returned for the 6 week assessment. Thus, enrolling 67 patients in each group ensures ≥ 52 patients (i.e. 39 CN-105-treated; 13 placebo treated) will complete the 6 week +/- 3 weeks postop assessment.

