5.4.2 Handling of Participant Withdrawals or Terminations

A recent phase I trial did not identify any specific adverse events or safety concerns with CN-105 (Guptill J et al, 2017). Nonetheless, if at any time during the dosing period, participant safety is considered at risk due to study agent-related adverse events per the judgement of the external Data Safety Monitoring Board (or DSMB+) and the PI, then the study agent will be immediately discontinued. Although the DSMB+ is only scheduled to convene and review reports (including grade II or higher AE, and SAE information) at the completion of each 67 patient cohort, the PI may also request that the independent statistician prepare additional interim analyses and provide these to the DSMB+ at any time. For example, this may be useful and/or appropriate if there is a severe SAE (such as a patient death) and the PI wishes to have the DSMB+ review grade II or higher AE rates and data up to an including this severe SAE, and make interim recommendations to the study team.

Since CN-105 modulates the inflammatory response, it could theoretically impair the response to infection. Thus, in an abundance of caution, the study agent will be discontinued in any patient who develops any intracerebral or systemic infection.

If a participant has clinically significant laboratory and/or electrocardiographic abnormalities that are considered to be related to the study agent in the judgement of the Principal Investigator or the DSMB, study agent treatment discontinuation will be evaluated.

Primary study analyses will be conducted using intention to treat analysis (i.e. with patients included in the groups to which they were randomized even if they did not correctly receive all doses to which they were randomized); secondary analysis may be conducted using as treated analyses (i.e. with patients grouped by the drug doses actually received).

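### The 6-week cognitive index is tested by an unadjusted t-test in expected returners, with no baseline or dose-cohort adjustment and no stated handling of the roughly 20% without a score

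*Combined protocol and SAP*

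**What the plan says.** Under Cognitive Data Analysis, section 10.1.3 compares index change scores "between patients who receive CN-105 vs placebo using a 2-sided t-test". It names no covariates. Power is computed "with ≥ 117 CN-105 treated and ≥ 39 placebo treated patients", at two-sided alpha 0.05 and a stated 80%, "to detect a half SD difference (i.e. 0.1 units) in CCI score between CN-105 vs placebo treated patients". The SD of 0.21 is the cognitive-change SD from the investigators' earlier cohort study.

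Sections 4.1 and 10.2 show where 117 and 39 come from. "In each group of 67 patients, 50 will receive a given dose of CN-105 and 17 will receive placebo", so three cohorts give 150 and 51. In the earlier study about "80% of patients returned for the 6 week assessment", and the plan therefore counts on 39 + 13 = 52 completers per cohort. Section 10.2 calls the same completers 3-month completers; the match with section 4.1 shows that the 6-week visit is meant.

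Section 5.4.2 promises intention to treat for the primary study analyses, "with patients included in the groups to which they were randomized even if they did not correctly receive all doses". It does not mention a missing outcome. The only text on missing data, in section 12, sends queries to the site. Section 10.3.1 stratifies randomisation by dose cohort.

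**The concern.** A t-test in returners estimates the effect in all randomised patients only if, within each arm, failure to return is unrelated to cognitive change. The protocol gives reasons to doubt that:

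- Section 2.2 links delirium to long-term cognitive decline and to one-year mortality.
- Section 5.4.1 has the investigator withdraw participants consented through a representative if they are distressed or uncooperative.
- Section 4.1 sets no cognitive exclusion and expects about 20% of patients to have mild cognitive impairment or dementia.
- Section 10.1.3 sizes the delirium comparison for 40% on placebo and 25 points fewer on CN-105.

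If the drug works that way, the arms differ in the characteristic most likely to drive loss. Placebo then loses more of its worst scores and the observed benefit shrinks. Separately, the unadjusted test leaves out a baseline score and a stratification factor that are already recorded, and so gives up precision.

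**Working it through.** **Inputs from the plan.** SD 0.21; half-SD effect 0.105, rounded in the text to 0.1; returners 117 and 39; randomised 150 and 51; delirium 40% versus 15%.

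**1. The plan's own power.** Power ≈ Φ(δ/SE − 1.96), with SE = 0.21 × √(1/39 + 1/117) = 0.0388.
- δ = 0.105: 2.704 − 1.96 = 0.744, power 77.2% (exact t 76.7%).
- δ = 0.1: 2.575 − 1.96 = 0.615, power 73.1% (exact t 72.6%).

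The stated 80% does not reproduce at 117 and 39, so there is little slack. The figure is already net of the expected loss: 156/201 = 77.6% return. What follows is additional to that loss.

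**2. Selective return.** Work in SD units, taking the plan's SD as the overall SD. Assumptions not in the documents: delirious patients score 1 SD worse, the total true effect is 0.50 SD, and return depends only on delirium. The part of the effect not acting through delirium is 0.50 − 1 × (0.40 − 0.15) = 0.25. The difference seen in returners is 0.25 + (qP − qC), where qP and qC are the delirious fractions among placebo and CN-105 returners.

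*Return 68% delirious, 88% not.*
- Placebo return: 0.4 × 0.68 + 0.6 × 0.88 = 0.80; qP = 0.272/0.80 = 0.34.
- CN-105 return: 0.15 × 0.68 + 0.85 × 0.88 = 0.85; qC = 0.102/0.85 = 0.12.
- Observed difference: 0.25 + 0.22 = 0.47 SD.
- Returners: 51 × 0.80 = 40.8 and 150 × 0.85 = 127.5; SE = 0.180; 0.47/0.180 − 1.96 = 0.65; power 74%.

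*Return 50% delirious, 90% not.*
- Placebo return 0.74, qP = 0.20/0.74 = 0.270. CN-105 return 0.84, qC = 0.075/0.84 = 0.089.
- Observed difference: 0.25 + 0.181 = 0.43 SD.
- Returners 37.7 and 126; SE = 0.186; power 64% (65% in simulation).

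*Equal return.* The difference stays at 0.50 SD. Power is about 77–78% (exact t 76.7% at 39/117, 78.3% at 40.8/120).

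*No drug effect on delirium (40% in both arms).* qP = qC at any pair of return rates, so the difference stays at 0.50 SD.

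**3. Range, with overall return held at 77.6% and a true difference of 0.105 index units.**

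| Deficit with delirium | Return if delirious | Observed difference | Power |
|---|---|---|---|
| 0.5 SD | 60% | 0.101 | 73% |
| 0.5 SD | 40% | 0.095 | 66% |
| 1 SD | 60% | 0.097 | 70% |
| 1 SD | 40% | 0.086 | 57% |

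**4. Gain from adjustment alone.** Assume a baseline-change correlation of −0.3 (not in the documents). Residual variance falls by the factor 1 − 0.09 = 0.91, and 0.50 SD becomes 0.50/√0.91 = 0.524 residual SD. At 39/117 the exact-t power rises from 76.7% to 80.4%, about 3–4 points. This does not depend on why patients fail to return.

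**5. What using delirium recovers.** Under the step 2 assumptions, weighting the delirium strata back to their randomised proportions gives 0.25 + 1 × (0.40 − 0.15) = 0.50 SD, the true effect.

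**The case against.** A reader might infer that the plan contradicts its own claim of intention to treat. The documents do not support that. Section 5.4.2 applies the principle to primary study analyses and defines it by randomised group despite missed doses. The cognitive index is a secondary endpoint. Section 10.1.3 does use the term primary analysis within a secondary endpoint, so the scope is unclear, but the result is a gap in the definition and not a contradiction.

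A reader might also infer that the t-test is bound to be biased, or could produce a false positive. Shrinkage needs three things together: a drug effect on delirium, worse scores in delirious patients, and lower return among them. The documents give no return rate by delirium status and no size for the deficit. With no drug effect on delirium or cognition, simulation at 50% versus 90% return showed no bias and a rejection rate of about 5%. In this mechanism the error is conservative.

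The plan also works to limit loss. It allows remote testing (sections 4.1 and 7.1.3), pays for transport (section 5.3) and encourages return after study agent is stopped (section 5.4.1). This is a secondary endpoint in a trial whose primary aim is safety. Multiple imputation is one choice among several, and it needs a rule for deaths and withdrawals.

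All of this stands and limits the size of the point. It does not supply the missing rule, since the plan still budgets for about 20% without a score, and it does not justify leaving out the baseline score and cohort.

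**Conclusion.** The point holds as a gap in the analysis specification. The main cognitive analysis is an unadjusted comparison of expected returners, with no missing-outcome method and no sensitivity analysis.

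The bias is conditional. In the milder scenario it is about 0.03 SD, with power of 74% against 77–78% under equal return. In the stress case it is about 0.07 SD, with power of 64–65%. Both rest on an assumed 1 SD deficit with delirium, assumed return rates and the plan's hoped-for delirium effect. The separate gain of 3–4 points from adjustment rests on an assumed correlation of −0.3.

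The change is worth making: it is cheap, and the adjustment is useful whichever way patients are lost. The documents do not show that selective return will occur.

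**What to change.** 1. Make the main analysis of the cognitive index a linear model for 6-week change with treatment, baseline index and dose cohort.
2. Before unblinding, pre-specify an analysis of all randomised patients that handles missing 6-week scores using baseline tests and in-hospital delirium, for example multiple imputation that also includes arm, age and cohort. State how deaths and withdrawals are treated. Use delirium only to handle missing scores: it arises after randomisation, and as a covariate in the outcome model it would remove part of the effect.
3. Add a delta-shift sensitivity analysis in which non-returners are assumed to have done worse.
4. Report return by arm and by delirium status.
5. Keep the unadjusted t-test in completers as supportive.
6. State which analysis set applies to secondary endpoints, and extend the wording in section 5.4.2 to missing outcomes.

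The cost is analysis-plan wording and modest programming. The baseline battery, twice-daily delirium assessments and cohort are already collected, and section 10.3.2 keeps the primary statistician blinded until database lock. The small downside is that the imputation model must be fixed in advance.
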